4.2. Study Endpoints

4.2.1. Primary Efficacy Endpoint (In Infant Subjects)

- Percentages of infants with medically-significant RSV LRTI from delivery through 90, 120, 150, and 180 days of life, as defined by:
 - The presence of RSV infection confirmed by detection of the RSV genome by RT-PCR on respiratory secretions (obtained within the continuous illness episode which fulfills the other criteria listed below); AND
 - At least one manifestation of lower respiratory tract infection (LRTI) from among the following: cough, nasal flaring, lower chest wall indrawing, subcostal retractions, stridor, rales, rhonchi, wheezing, crackles/crepitations, or observed apnea; AND
 - Evidence of medical significance as defined by the presence of:
 - EITHER hypoxemia (peripheral oxygen saturation [SpO_2] < 95% at sea level or < 92% at altitudes > 1800 meters) OR
 - Tachypnea (\geq 70 breaths per minute [bpm] in infants 0 to 59 days of age and \geq 60 bpm in infants \geq 60 days of age).

Data elements supporting the three (3) criteria for a primary endpoint case will be present within the start and stop dates of a continuous illness episode and derived from clinical observations (LRTI signs and symptoms and respiratory rates) made by qualified clinical trial site staff, pulse oximetry performed by site personnel using a Masimo RAD-5 pulse oximeter supplied by the sponsor, and RSV detection based on study-specified RT-PCR performed by the validated GenMark eSensor assay in place at the central laboratory (Marshfield Clinic Research Institute, Marshfield, Wisconsin).

A Clinical Endpoint Adjudication Committee (CEAC) composed of expert pediatricians (see Section 10.2) will carry out a blinded review of all potential primary endpoint cases to determine if they fulfill the primary endpoint criteria in a temporally plausible relationship consistent with RSV disease as observed in clinical practice. Only CEAC-confirmed cases will be used for the primary endpoint.

4.2.2. Secondary Efficacy Endpoints (In Infant Subjects)

- Percentages of infants with RSV LRTI with severe hypoxemia (SpO_2 < 92% at sea level or < 87% at altitudes > 1800 meters) OR the documented use of oxygen by high flow nasal cannula OR a requirement for continuous positive airway pressure (CPAP) OR bilevel positive airway pressure (BiPAP) OR Bubble CPAP OR bag-mask ventilation OR intubation with subsequent mechanical (or manual) ventilation OR extracorporeal membrane oxygenation (ECMO) from delivery through 90, 120, 150, and 180 days of life. An event is considered RSV LRTI with severe hypoxemia if all parameters outlined below are present during a continuous symptomatic illness episode:

- RSV infection as confirmed by detection of the RSV genome by RT-PCR, AND
- At least one manifestation of lower respiratory tract infection (LRTI) from among the following: cough, nasal flaring, lower chest wall indrawing, subcostal retractions, stridor, rales, rhonchi, wheezing, crackles/crepitations, or observed apnea, AND
- Evidence of severe hypoxemia or the requirement for respiratory support as defined by the presence of:
 - EITHER severe hypoxemia (peripheral oxygen saturation [SpO₂] < 92% at sea level or < 87% at altitudes > 1800 meters) OR
 - The documented use of oxygen by high flow nasal cannula OR continuous positive airway pressure (CPAP) OR bilevel positive airway pressure (BiPAP) OR Bubble CPAP OR bag-mask ventilation OR intubation with subsequent mechanical (or manual) ventilation OR extracorporeal membrane oxygenation (ECMO).
- Percentages of infants with RSV LRTI with hospitalization from delivery through 90, 120, 150, and 180 days of life. An event is considered RSV LRTI hospitalization if all parameters outlined below are present during a continuous symptomatic illness episode:
 - RSV infection as confirmed by detection of the RSV genome by RT-PCR, AND
 - At least one manifestation of lower respiratory tract infection (LRTI) from among the following: cough, nasal flaring, lower chest wall indrawing, subcostal retractions, stridor, rales, rhonchi, wheezing, crackles/crepitations, or observed apnea, AND
 - Documented hospitalization.

Data elements supporting the criteria for secondary endpoint cases will be present within the start and stop dates of a continuous illness episode and derived from clinical observations (LRTI signs and symptoms and respiratory rates) made by qualified clinical trial site staff, pulse oximetry performed by site personnel using a Masimo RAD-5 pulse oximeter supplied by the sponsor, and RSV detection based on study-specified RT-PCR performed by the validated GenMark eSensor assay in place at the central laboratory (Marshfield Clinic Research Institute, Marshfield, Wisconsin). Evidence of hospitalization and/or in-hospital use of high-flow nasal cannula, CPAP, BiPAP, bubble CPAP, intubation, or mechanical/manual ventilation or ECMO will be supported by hospital records obtained by the clinical site staff.

A Clinical Endpoint Adjudication Committee (CEAC) composed of expert pediatricians (see Section 10.2) will carry out a blinded review of all potential secondary endpoint cases to determine if they fulfill the relevant endpoint criteria in a temporally plausible relationship consistent with RSV disease as observed in clinical practice. Only CEAC-confirmed cases will be used for secondary endpoints.

4.2.3. Exploratory Efficacy Endpoints in Infant and Maternal Subjects

- Percentages of infants with medically-significant RSV LRTI from delivery through 90, 120, 150 and 180 days of life defined as per the primary efficacy endpoint with the exception that evidence of RSV infection, LRTI, hypoxemia, and/or tachypnea may be based on either or both of the observations of the clinical site staff using sponsor-supplied devices and

diagnostic tests OR review and abstraction of medical records for infants undergoing hospitalization for a respiratory serious adverse event.

- Percentages of infants with RSV LRTI with EITHER severe hypoxemia ($\text{SpO}_2 < 92\%$ at sea level or $< 87\%$ at altitudes > 1800 meters) OR the documented use of oxygen by high flow nasal cannula OR continuous positive airway pressure (CPAP) OR bilevel positive airway pressure (BiPAP) OR Bubble CPAP OR bag-mask ventilation OR intubation with subsequent mechanical (or manual) ventilation OR extracorporeal membrane oxygenation (ECMO) from delivery through 90, 120, 150, and 180 days of life defined as per the corresponding secondary efficacy endpoint with the exception that evidence of RSV infection, LRTI, severe hypoxemia, and/or respiratory support may be based on either or both of the observations of the clinical site staff using sponsor-supplied devices and diagnostic tests OR review and abstraction of medical records for infants undergoing hospitalization for a respiratory serious adverse event.
- Percentages of infants with RSV LRTI requiring hospitalization from delivery through 90, 120, 150, and 180 days of life defined as per the corresponding secondary efficacy endpoint with the exception that evidence of RSV infection and LRTI may be based on either or both of the observations of the clinical site staff using sponsor-supplied devices and diagnostic tests OR review and abstraction of medical records for infants undergoing hospitalization for a respiratory serious adverse event.
- Percentages of infants with RSV LRTI associated with EITHER hypoxemia (peripheral oxygen saturation [SpO_2] $< 95\%$ at sea level or $< 92\%$ at altitudes > 1800 meters) OR tachypnea (≥ 60 bpm for infants 0 to 59 days of age or ≥ 50 bpm for infants ≥ 60 days of age [WHO Handbook, Integrated Management of Childhood Illness criteria for tachypnea]) from delivery through 90, 120, 150, and 180 days of life. Data concerning documentation of RSV infection, LRTI symptoms and signs, hypoxemia and/or tachypnea may be obtained from the observations of the clinical site staff OR review and abstraction of medical records for infants undergoing hospitalization for a respiratory serious adverse event.
- Percentages of infants with RSV LRTI resulting in death from delivery through 90, 120, 150, and 180 days of life. Evidence of RSV infection and LRTI may be based on either or both of the observations of the clinical site staff using sponsor-supplied devices and diagnostic tests OR review and abstraction of medical records for infants undergoing hospitalization for a respiratory serious adverse event.
- Percentages of infants with RSV LRTI (all severities) from delivery through 90, 120, 150, and 180 days of life. Evidence of RSV infection and LRTI may be based on either or both of the observations of the clinical site staff using sponsor-supplied devices and diagnostic tests OR review and abstraction of medical records for infants undergoing hospitalization for a respiratory serious adverse event.
- Counts and incidence rates of infant healthcare interventions associated with wheezing through the first year of life.
- Percentages of maternal subjects with RSV-related respiratory illness as observed by the clinical study staff and detected by active and passive surveillance from vaccination through six months after delivery, overall and by pathogen(s).

- Percentages of infant subjects with all-cause LRTI, with or without tachypnea, hypoxemia, or severe hypoxemia, as detected by active and passive surveillance from vaccination through six months after delivery, overall and by pathogen(s).
- Percentages of infant and maternal subjects with non-RSV respiratory viruses, overall and by pathogen(s), through six months after delivery.

A Clinical Endpoint Adjudication Committee (CEAC) composed of expert pediatricians (see Section 10.2) will carry out a blinded review of all potential exploratory endpoint cases involving RSV LRTI in infants to determine if they fulfill the relevant endpoint criteria in a temporally plausible relationship consistent with RSV disease as observed in clinical practice. Only CEAC-confirmed cases will be used for exploratory endpoints.

4.2.3.1. Data Sources for Exploratory Efficacy Endpoints

Exploratory efficacy endpoints will be supported by any combination of data derived from the following sources of data:

- The observations of RSV genome detection by RT-PCR via the validated assay at the central laboratory (Marshfield Clinic Research Institute, Marshfield, Wisconsin), the verification of RSV LRTI symptoms and signs and respiratory rates per qualified site staff, and pulse oximetry using a Masimo Rad-5 pulse oximeter provided by the sponsor, AND
- Documented healthcare records available to the site personnel which capture clinical observations of respiratory rate and LRTI symptoms and signs, oxygen saturation using non-sponsor provided pulse oximeters, and locally performed RT-PCR detection of RSV genome and any oxygen interventions utilized to support hypoxemic infants. These data will be derived from records of hospitalizations or emergency room observations. The above information will be recorded in an eCRF and monitored against source documentation. Wherever possible, the name, model, and manufacturer of pulse oximeters and RSV diagnostic tests will be collected.

4.2.4. Immunogenicity Endpoints (In Maternal and Infant Subjects as Stated)

- Serum immunoglobulin G (IgG) antibody concentrations specific for the F protein antigen measured by enzyme-linked immunosorbent assay (ELISA) and serum concentrations of antibodies competitive with palivizumab for binding to the RSV F protein. Derived/calculated endpoints based on these data will include geometric mean concentrations as ELISA Units (GMEU) or $\mu\text{g}/\text{mL}$ as appropriate, geometric mean fold-rise (GMFR), proportion of subjects with ≥ 2 -fold and ≥ 4 -fold increases in concentration from baseline (seroconversion rate, SCR [maternal subjects only]), and seroresponse rate (SRR). Analyses will be used to evaluate:
 - Immunogenicity through six months post-delivery in maternal subjects.
 - Transplacental transfer of maternal antibodies specific for RSV described as a ratio of levels in maternal and cord blood at delivery.

- Infant RSV-specific antibody decay during the first six months of life relative to cord blood levels.
- Immune correlate of risk of RSV LRTI in infants based on anti-RSV F protein IgG or palivizumab-competitive antibody responses in the infant and/or cord blood, and maternal subjects at delivery.
- Serum microneutralization (MN) titers against RSV/A and B in maternal and infant subjects at select time-points may be generated for a subset of the population using the derived/calculated endpoints previously referenced, but based on geometric mean titer (GMT). An external laboratory, whose personnel are blinded to study treatment, will perform RSV/A and B MN testing during study conduct and after Day 180 unblinding. Final MN results, because of their time-consuming nature, may be provided as one or more sequential addenda to the main study report.

4.3. Safety Endpoints

4.3.1. In All Infant Subjects

- Percentages of term (≥ 37 weeks gestational age), healthy infants appropriate for gestational age (as determined by ultrasound gestational age assessment), APGAR scores, length, birth weight, frontal-occipital head circumference (FOC), and physical examination at birth.
- Percentages of infants with AEs and SAEs (with special attention to congenital anomalies, respiratory failure other than RSV-associated hospitalization; neonatal death; infant death; sudden infant death syndrome; asphyxia; neonatal or hypoxic-ischemic encephalopathy; or other adverse events or complications of adverse events that necessitate hospitalization) during the neonatal period and through the first year of life.
- Percentages of infants with unsolicited adverse events (including abnormalities detected in routine metabolic screening blood and neonatal hearing tests), unscheduled medical visits for adverse events, and serious adverse events through the first year of life.
- Percentages of infants with developmental delay, as measured by the outcome of testing using a validated developmental scale at six months and at one year, in infants of RSV F vaccinees as compared to placebo.

4.3.2. In Maternal Subjects

- Percentages of subjects with solicited injection site and systemic reactogenicity within seven days of vaccination.
- Percentages of subjects with unsolicited (local and systemic) adverse events (AEs), unscheduled medically-attended adverse events (MAEs), significant new medical conditions (SNMCs), and serious adverse events (SAEs) through delivery and six (6) months thereafter.
- Clinical safety laboratory assessments of select serum chemistry and hematology parameters through delivery.

- Percentages of subjects with Caesarean, vaginal, or instrument-assisted vaginal modes of delivery.
- Percentages of subjects with post-immunization onset of specific complications of third-trimester pregnancy and delivery including (but not necessarily limited to):
 - Pregnancy complications:
 - Stillbirth,
 - Preterm birth (moderate to late preterm: 32 to < 37 weeks of gestation; very preterm: 28 to < 32 weeks of gestation),
 - Preterm premature rupture of membranes,
 - Placental abruption,
 - Hypertensive disorders of pregnancy including: gestational hypertension, pre-eclampsia/eclampsia,
 - Third-trimester hemorrhage, and
 - Gestational diabetes.
 - Labor and delivery complications:
 - Emergency Caesarean (C)-section for maternal or fetal indications,
 - Postpartum hemorrhage,
 - Chorioamnionitis, and
 - Maternal fever or infection.

5. ANALYSIS POPULATIONS

The subject populations to be evaluated and used for presentation and analysis of the data are defined in Sections 5.1 to 5.3. Unless otherwise specified, all maternal subjects and/or infants will be presented in treatment groups based on actual treatment received (RSV F Vaccine or Placebo).

5.1. Safety Population

- The maternal Safety Population (Safety-M) includes all maternal subjects who receive any test article. The infant Safety Population (Safety-I) includes all infants born live to maternal subjects who received any test article. The Safety Populations will be used for all safety analyses and will be analyzed based on treatment actually received (i.e., as randomized, unless conclusive documentation exists to confirm the mis-dosing of a subject AND the identity of the treatment actually received).

5.2. Intent-to-Treat Population

- Intent-to-treat Efficacy (ITT-EFF) Population – defined as all maternal subjects (ITT-EFF-M) and their infants (ITT-EFF-I) in the Safety Population for whom at least one post-treatment and post-partum, respectively, efficacy measurement is available as evidenced by collection of surveillance observations. The ITT-EFF Population will be analyzed as randomized.
- Intent-to-treat Immunogenicity (ITT-IMM) Population – defined as all maternal subjects (ITT-IMM-M) and their infants (ITT-IMM-I) in the Safety Population for whom at least one post-treatment immunogenicity measurement is available.

5.3. Per-Protocol Population

5.3.1. Per-Protocol Efficacy (PP-EFF) Populations

- The PP-EFF Populations will be the primary analysis populations for the efficacy analyses.
- PP-EFF for Maternal Subjects (PP-EFF-M) – defined as all maternal subjects who receive the test article and regimen to which they were randomized, have at least one post-treatment encounter documented during which active and/or passive surveillance activities for RSV-suspect illness can occur, and have no major protocol deviations affecting the primary efficacy outcomes as determined and documented by Novavax prior to database lock and unblinding.
- The Per-Protocol Population for infant subjects (PP-EFF-I) – defined as all infant subjects who: a) are \geq 37 weeks gestational age at birth, b) are born to maternal subjects who received a study injection as randomized and \geq 2 weeks prior to delivery, c) have not received prophylactic treatment with palivizumab between birth and Day 180 after delivery, d) have at least one documented post-partum contact during which active and/or passive surveillance activities for RSV-suspect illness can occur, and e) have no major protocol

deviations affecting the primary efficacy outcomes as determined and documented by Novavax prior to database lock and unblinding.

5.3.2. Per-Protocol Immunogenicity (PP-IMM) Populations

- The PP-IMM Populations will be the primary analysis populations for the immunogenicity analyses.
- PP-IMM for Maternal Subjects (PP-IMM-M) – defined as all maternal subjects who receive the test article and regimen to which they were randomized, provide baseline and delivery (within 72 hours of delivery) serology data, and have no major protocol deviations affecting the primary immunogenicity outcomes as determined and documented by Novavax prior to database lock and unblinding.
- PP-IMM for Infant Subjects (PP-IMM-I) – defined as all infant subjects who: a) are ≥ 37 weeks gestational age at birth, b) are born to maternal subjects who received a study injection as randomized and ≥ 2 weeks prior to delivery, c) have provided a cord blood specimen (or infant blood sample by venipuncture or heel stick within 72 hours of delivery as an acceptable substitute), d) have not received prophylactic treatment with palivizumab between birth and Day 180 after delivery, and e) have no major protocol deviations affecting the primary immunogenicity outcomes as determined and documented by Novavax prior to database lock and unblinding.

5.3.3. Protocol Deviations

Subjects with major protocol deviations may be excluded from the PP analysis population. Protocol deviations that meet the threshold of “major” will be determined prior to unblinding, at the Sponsor’s discretion. The Sponsor or designee will be responsible for producing a final deviation file prior to database lock. This file will provide a description of each protocol deviation and will clearly identify whether or not a deviation warrants exclusion from the PP analysis population. All protocol deviations will be presented in a data listing, with a flag to indicate if a deviation was considered major and resulted in the exclusion of the subject from the PP analysis population.

5.3.3.1. Major Protocol Deviations Assessment

Prior to unblinding, the Novavax Clinical Development personnel will assess protocol deviations and create a consensus final protocol deviations assessment file. Protocol deviations deemed to have a likely effect on the primary efficacy or immunogenicity outcomes, or demonstrating an important failure of Good Clinical Practice, will exclude those subjects from one or both of the PP analysis populations. In general, the following will be deemed “major:”

- Failure to obtain completely executed and documented informed consent for both mother and infant.
- Failure to receive, or document receipt of, all study treatments as randomized and within the protocol-specified window.

- Failure to provide a sample from the maternal subject for serologic analysis at baseline and at delivery, and a cord blood (or acceptable alternative) and at least one later anti-RSV F serology time-point from the infant within the protocol-specified window. “Failure to provide a sample” will be interpreted based on the protocol visit windows, i.e., provision of one or more sample(s) outside the windows may constitute grounds for a deviation if deemed significant by the medical lead.
- Receipt of any non-protocol vaccine, within 14 days of study test article administration.
- Receipt of any immunosuppressive medication before delivery.

Other deviations deemed likely by the Sponsor to degrade the immune response to the test article, or to indicate a serious departure from Good Clinical Practice, may be exclusionary from the PP population, but must be documented before unblinding for the D+180 analysis.

6. SUBJECT DISPOSITION

The number of maternal subjects consented, randomized, and vaccinated will be presented by treatment group according to the test article received (Placebo or RSV F vaccine) at Day 0 for all subjects. Infant subjects will also be presented according to the test article received by the maternal subjects in all tables and listings.

The number (percentage) of maternal subjects who have completed the study through delivery and through D+180, and the number of infants who completed the study through D+180 and D+364 of life will be presented by treatment group for all subjects in the Safety Population. The number of maternal subjects who discontinue the study prior to delivery and between delivery and D+180 will be presented. Similarly, the number of infant subjects who discontinue the study prior to D+180 and D+364 of life, and the reason for discontinuation (e.g., withdrawal of consent, loss to follow-up, death, etc.) will be presented. Study completion status of the maternal subjects through delivery and D+180, and infant subjects through D+180 and D+364 of life will be determined based on delivery visit date for the maternal subject and the D+180 study visit date for the infant subject. Study completion status through D+364 will be determined based on the D+364 End of Study (EOS) electronic case report form (eCRF).

A listing of all subjects in the Safety Population who are discontinued will be presented by treatment group, reason for discontinuation, and day of last study contact. Day of last study contact for the maternal subjects is the date of study discontinuation (as recorded on the Study Day 180 post-delivery/eCRF) minus Day 0 vaccination date. The date of last study contact for the infant will be calculated as follows: date of study discontinuation (as recorded post-delivery on the Study Day 364/EOS eCRF) minus the delivery date. Infants of maternal subjects who discontinue prior to delivery will be deemed to have discontinued at the same time as the maternal subjects; tabulation of infant subjects discontinued in this manner will not be performed as no post-natal data exists for these infants.

A listing of all subjects in the Safety Population with one or more protocol deviations recorded through D+180 for mothers/infants, and updated at the end of the study, will be provided and will include: treatment group, study day associated with the deviation (as provided on the protocol deviation log if available), and protocol deviation category (as described below). All deviations from protocol procedures, evaluations, and visits will be documented throughout the course of the study. The following categories of protocol deviations are to be recorded on a per-subject basis:

Maternal Subject Deviation Categories:

- Diary Compliance
- Inclusion Criteria
- Missed Visit
- Randomization Error
- Excluded Concomitant Medication or Procedure
- RSV Surveillance Specimen Collection Not Done
- Exclusion Criteria
- Informed Consent
- Out of Window Visit
- Study Procedure Not Done
- Vaccination Error
- Other

Infant Subject Deviation Categories:

- Informed Consent
- Missed Visit
- Out of Window Visit
- Randomization Error
- Study Procedure Not Done
- Other
- RSV Surveillance Specimen Collection Not Done

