6.1.1.9 D+180 (\pm 14 days) – In-clinic or Home Post-delivery Follow-up Visit

Maternal subjects will return to the clinic or will be evaluated by study staff at a home visit on approximately 180 days post-delivery for the following procedures:

- Vital sign collection (heart rate, blood pressure, respiratory rate, and axillary body temperature).
- Pregnancy testing. Note that a positive result will trigger additional follow-up to monitor the outcome of this pregnancy.
- Query for any unsolicited AEs (including MAEs, SNMCs, and SAEs) experienced and concomitant medications taken for these events since the last visit. *Note that a physical exam may also be performed at the investigator's discretion to evaluate any adverse event reported.* Maternal subjects will also be queried regarding symptoms suggestive of RSV infection and, if symptom onset is within seven (7) days, will undergo a sampling of upper respiratory secretions for detection of respiratory viruses if specific events are present (see **RSV Illness Surveillance** procedures in Section 6.2).
- Blood draw (20 mL) for post-vaccination RSV serology.

This visit will mark the end of study participation for the maternal subject. However, maternal subjects with ongoing respiratory episodes will be contacted weekly by telephone/SMS contact and followed until symptoms have resolved or have returned to baseline. In addition, maternal subjects with a positive pregnancy result will be followed for safety through the time of delivery to determine the outcome of this pregnancy.

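### The SAP names only the delivery visit date as the source for maternal completion through D+180, so the maternal disposition table does not reconcile

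*SAP*

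**What the plan says.** SAP Section 6 plans counts and percentages of mothers completing through delivery and through D+180, and counts of infants completing through D+180 and D+364. These "will be presented by treatment group for all subjects in the Safety Population".

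The rule for deciding status follows in the same paragraph. Its subject is "Study completion status of the maternal subjects through delivery and D+180, and infant subjects through D+180 and D+364 of life", and status "will be determined based on delivery visit date for the maternal subject and the D+180 study visit date for the infant subject". So four statuses are given two dates. The next sentence assigns D+364 status to the D+364 end-of-study form.

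The same paragraph also counts losses: "The number of maternal subjects who discontinue the study prior to delivery and between delivery and D+180 will be presented". The following paragraph adds a listing of Safety Population subjects "who are discontinued will be presented by treatment group, reason for discontinuation, and day of last study contact". For mothers, the day of last contact in that listing is the "date of study discontinuation (as recorded on the Study Day 180 post-delivery/eCRF) minus Day 0 vaccination date".

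Protocol 6.1.1.9 says of the maternal D+180 visit: "This visit will mark the end of study participation for the maternal subject".

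**The concern.** A delivery visit date shows that a woman reached delivery. It cannot show that she was still in the study about six months later. If the rule is programmed as it stands, the two maternal completion rows hold the same number in each arm, and the second row carries no information on follow-up after delivery.

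That row is meant to show maternal retention over the period in which maternal adverse events, medically-attended events, significant new medical conditions and serious adverse events are collected up to six months after delivery. The exploratory objective on maternal RSV illness runs to the same point. A reader who takes the completion row at face value would believe follow-up to be more complete than it was, and would then find a discontinuation count in the same table that contradicts it.

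**Working it through.** The plan gives no figure to reproduce, and no post-delivery loss rate is stated in either document. The check is one of logic and bookkeeping.

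**Which status has which source (SAP Section 6)**

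| Status | Source in the rule | Later sentence that changes it |
|---|---|---|
| Mother, through delivery | Delivery visit date | None needed |
| Mother, through D+180 | Delivery visit date | None |
| Infant, through D+180 | Infant D+180 visit date | None needed |
| Infant, through D+364 | Infant D+180 visit date | Yes: D+364 end-of-study form |

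The infant D+364 entry is corrected by the next sentence. The maternal D+180 entry is not corrected anywhere in the section.

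**Does the table add up?** Within one arm, let

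- S = mothers in the Safety Population,
- B = those with a delivery visit date,
- X = those among B who leave between delivery and D+180.

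For simplicity, assume every mother without a delivery visit date is counted as discontinued before delivery.

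Under the rule as written:

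- completed through delivery = B
- completed through D+180 = B
- discontinued before delivery = S − B
- discontinued between delivery and D+180 = X

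Completers through D+180 plus all discontinuers = B + (S − B) + X = S + X.

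The total should be S. It is too large by X, because each of those X women is counted twice. With the D+180 row based on the D+180 form, completers are B − X, and the sum is (B − X) + (S − B) + X = S.

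The table therefore reconciles only if X = 0, that is, if no woman leaves after delivery.

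**Can the loss still be found?**

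- The delivery-to-D+180 discontinuation count gives X. Its own sentence does not mention treatment group, but the opening of SAP Section 5 makes presentation by treatment group the default unless otherwise specified, and SAP Section 16 says much the same for summary tabulations.
- The listing of discontinued subjects gives treatment group, reason and day of last contact. For mothers it is dated from the Day 180 post-delivery form, not from the delivery visit.

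X is therefore available by arm, and the correct D+180 completion count, B − X, can be derived by hand.

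**Does anything else depend on the rule?** In SAP Section 5, the maternal Safety Population is defined by receipt of test article. The maternal intent-to-treat and per-protocol efficacy populations rest on having at least one post-treatment surveillance observation or encounter; the per-protocol set also requires treatment as randomized and no major deviation. None of these definitions refers to completion status, and neither does the primary infant analysis.

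**The case against.** The best defence is that the sentence is shorthand. It packs four statuses into two dates, and the next sentence shows that it was not meant literally for infants at D+364. The paragraph asks separately for women lost between delivery and D+180, and the listing takes the maternal discontinuation date from the Day 180 form, so the authors plainly meant to track post-delivery loss. A sensible programmer would use that form for the D+180 row as well.

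This stands as an account of intent, but it does not supply the missing rule. If the delivery date is read as applying only to the delivery milestone, maternal D+180 completion has no stated source and the programmer must choose one. If it is read as written, the count is wrong. Either way the sentence needs correcting.

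The defence is right about consequence. A reader might infer that loss after delivery cannot be seen by arm. The documents do not support that: the discontinuation count and the listing both show it. A reader might also infer that infant D+364 status is governed by two competing rules, but the later and more specific sentence settles it. Nor is it an error to decide infant D+180 completion from the infant D+180 visit. That is a defensible visit-based definition, and counting any later contact as completion would be a different convention, not a correction.

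**Conclusion.** The point holds as a minor error in a descriptive table. SAP Section 6 gives no valid source for maternal completion through D+180. Applied as written, it makes the D+180 row a copy of the delivery row in each arm and places post-delivery leavers in both the completed and the discontinued counts.

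The size of the error is the number of women who leave between delivery and D+180. No loss rate is given, so no figure can be put on it; multiplying an assumed rate by enrolment would add nothing. The conclusion rests on the literal wording of the rule and on the absence of any other maternal D+180 rule in that section. No efficacy or safety analysis set, endpoint, estimate or test changes.

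**What to change.** Make three edits in SAP Section 6:

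1. Base maternal completion through delivery on the delivery visit.
2. Base maternal completion through D+180 on the Study Day 180 post-delivery eCRF, which the section already uses to date maternal discontinuation.
3. Remove D+364 from the sentence that states the date sources, leaving the next sentence to govern it.

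The infant D+180 rule can stay as it is. The cost is a sentence or two. No new data or form is needed, and the maternal table will then reconcile.
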